## ABBREVIATIONS / GLOSSARY

Abbreviation	Description
AE	Adverse Event
AES	Advanced Encryption Standard
BMI	Body Mass Index
BBT-RS	Big Baby Trial Research System
CASE	Complier Average Causal Effect
CI	Confidence Interval
CONSORT	Consolidated Standards Of Reporting Trials
CSRL	Clinical Sciences Research Laboratories
CRF	Case Report Form
DM(E)C	Data Monitoring And Ethics Committee
EFW	Estimated Fetal Weight
EQ-5D-5L	European Quality of Life Five Dimension Five Level Scale
GAP	Growth Assessment Protocol
GCP	Good Clinical Practice
GP	General Practitioner
GROW	Gestation Related Optimal Weight
HTA	Health Technology Assessment
LTFU	Lost To Follow Up
IRAS	Integrated Research Application System
ISRCTN	International Standard Randomised Controlled Trial Number
LGA	Large for Gestational Age
MSLC	Maternity Service Liaison Committee
NHS	National Health Service
NICE	The National Institute for Health Care Excellence
NICHD	National Institutes of Child Health and Human Development
NICU	Neonatal Intensive Care Unit
PEN	Potential Eligibility Number
PGP	Pretty Good Privacy Encryption
PNI	Perinatal Institute
PI	Principal Investigator
PIS	Participant Information Sheet
PPI	Patient and Public Involvement
QALY	Quality-Adjusted Life Year
QoL	Quality of Life
R&D	Research and Development

RCM	The Royal College of Midwives
RCOG	The Royal College of Obstetricians and Gynaecologists
RCPCH	The Royal College of Paediatrics and Child Health
RCT	Randomised Controlled Trial
SAE	Serious Adverse Event
SD	Shoulder Dystocia
SGA	Small for Gestational Age
SOP	Standard Operating Procedure
SSQ	Six Simple Questions
TMG	Trial Management Group
TSC	Trial Steering Committee
VPN	Virtual Private Network
WCTU	Warwick Clinical Trials Unit

## 1. BACKGROUND

### 1.1 Epidemiology and burden of the condition

Shoulder dystocia (SD) is defined as a vaginal cephalic delivery that requires additional obstetric manoeuvres to deliver the fetus after the head has delivered and gentle traction has failed. Potential complications for impacted shoulder for the mother include haemorrhage and third and fourth-degree laceration, and for the neonate include fracture of the clavicle or humerus, temporary or permanent brachial plexus injury, hypoxic ischaemic encephalopathy, and neonatal death. Shoulder dystocia causes physical and psychological trauma to both mother and her baby, as it is an obstetric emergency which requires rapid response and intervention, often with limited time to inform and/or explain to the woman and her birth companion what is happening.

Apart from adverse maternal and perinatal effects, shoulder dystocia is also one of the most common reasons for litigation, with settlement of 250 cases from 2000 to 2010 having cost over £100 Million, or approx. £400,000 per case.

Most but not all cases of SD occur in pregnancies where babies are macrosomic, variously defined as above 4kg, 4.5kg, or >90th customised weight for gestational age centile.

Appropriate management of the condition includes clinical awareness, trained staff and appropriate management protocols and emergency drills. Preventive measures start with antenatal awareness of risk factors, including maternal obesity and diabetes and fetal growth and size.

### 1.2 Definitions for macrosomia

The Royal College of Obstetricians and Gynaecologists (RCOG) Guidelines 1 identified macrosomia >4.5kg as the weight related pre-labour risk factor for shoulder dystocia and this cut-off limit has been confirmed to have the strongest association in a large study since, using an outcome based approach.

### 1.3 Measuring macrosomia

A weight-for-gestational age limit (large for gestational age, LGA) is required for antenatal prediction, where the critical weight limit is not yet reached but the fetus is growing in a steep trajectory towards it. To consider a fetal/neonatal weight in relation to maternal size, a customised standard is needed and the customised GROW 90th customised centile has now been found in several studies to identify a significant number of additional pregnancies as being at risk which were not recognised by conventional standards for macrosomia, including absolute weight limits (4 or 4.5kg) and population based weight-for-gestational age centiles.

 Typically, babies that were large according to GROW centiles only, tended to weigh less but were still large in relation to the size of the mother. Importantly, GROW accounts for maternal height, widely thought to be a factor in shoulder dystocia. Furthermore GROW was found to be a better predictor for shoulder dystocia than the UK-WHO birthweight standard. An analysis of data from the international SCOPE study cohort found that adverse birth outcomes were not increased in babies that were appropriately grown by customised standards, even if they appeared to have a birthweight which was high according to conventional weight limits or population based centiles. In our NHS database, 84% of babies with birthweight over

4.5kg, are also identified as LGA by customised GROW centiles; in contrast, using 4.5kg as the cut off will miss another 78% of babies that are LGA using GROW centiles.

Earlier delivery should reduce the baby's weight at birth and hence mitigate the main risk factor. For there to be a meaningful difference in the incidence of shoulder dystocia, and to ensure that any possible benefit is not overlooked, we are aiming for an average birthweight difference of 300g or more. This is consistent with the largest preceding RCT where the early delivery protocol resulted in a reduction of birthweight by 287g (CI:336-238g), however the gestational age difference was not stated.

Looking at the West Midlands database (N=161,936) we ascertained that the weekly increment of weight in LGA pregnancies is approximately 200g. We are aiming for a mean difference in gestational age at delivery of 1.5 weeks to reflect a birthweight difference of 300g. This would be made possible by induction from 38+0 to 38+4 weeks gestation, or as soon as possible thereafter, before the expected onset of labour in the control group which, from the West Midlands Database is on average 39+4 weeks gestation. Induction before 38+0 would further reduce the risk of shoulder dystocia, but would increase risks of prematurity for the baby.

However it is uncertain whether this strategy would actually work, whether shoulder dystocia and its associated complications for mother and baby would actually be reduced, and whether there would be an increase in important side effects such as caesarean sections and associated maternal morbidity. Induction of labour can also be traumatic as it can be associated with prolonged painful labour, and may lead to unplanned operative delivery.

#### 1.4 Summary of the existing evidence

Research into early delivery is timely, in light of conflicting messages from RCOG Guideline on one hand, which found little evidence in favour of early delivery of the LGA fetus, and a recent Cochrane review as well as a systematic review and meta-analysis which found in favour of such intervention. Both of these reviews were largely based on the result of the recent French RCT which contributed most cases in the analysis.

Additional urgency to address this issue exists because of a steep increase in maternal obesity over recent years, and evidence that maternal obesity is associated with a slowing of progress of labour. Although routine data on the prevalence of maternal obesity are not collected in the UK, around half of all women of reproductive age (aged 16-44) are overweight or obese. Women who commence pregnancy overweight or obese, or gain excessive gestational weight in pregnancy, have greater risk of fetal macrosomia.

Given the current lack of evidence of benefit of interventions to manage maternal weight in pregnancy and trials ongoing which are assessing postnatal interventions, evidence is urgently needed on whether induction of labour could reduce maternal and fetal complications and minimise or prevent birth trauma when fetal macrosomia is detected.

#### 1.5 Research question

Does induction of labour at 38+0 to 38+4 weeks gestation, in pregnancies with a large for gestational age fetuses, reduce the incidence of shoulder dystocia?

### 1.6 Need for a trial

An investigation into the value of a preventative intervention in the NHS is urgently required before practice based on limited evidence is adopted in the UK. An intervention which could increase vaginal births may result in better longer-term outcomes for women and their infants, with reduced risk of maternal and fetal birth injuries and potential reduction in subsequent NHS costs, although evidence of this is also needed. Although previous trials have considered management in terms of clinical outcomes, studies have failed to address important outcomes for women.

We are not aware of any evidence of women's experiences of being informed that their pregnancy is large for dates, if and how options for management were discussed with them, the impacts on their perceived physical and psychological health, their infant's health, decisions about infant feeding or their satisfaction with birth. Furthermore, women's experiences and perspectives, of how labour and birth were discussed with them have not previously been considered, nor evidence of benefits and potential harms in the short and long term. This is particularly relevant as short-term follow-up could 'miss' important morbidity outcomes, particularly psychological consequences. It is also unknown how many women would accept such a protocol of earlier delivery, or indeed how many would be content to proceed with vaginal delivery rather than requesting caesarean section, once informed about the increased risk of a large for gestational age baby and associated risk.

It is important that a randomised control trial is performed to generate the data needed for women with large babies to make informed choices about their labour onset, likely mode of birth and potential shorter and longer-term impacts which may be associated with the option selected. This will support the need to explain all potential risks and benefits of management, highlighted by the recent Montgomery judgement, and current maternity policy, which emphasises the importance of involving women in all decisions about their care, to ensure that real 'choice' is truly offered (National Maternity Review England 2016).

### 1.7 Ethical considerations

In any trial involving pregnant women, consideration is needed on the ethical dimensions of the study. Most importantly, women joining the study need to be informed about the potential risk and benefits of joining the study, and the possible risks and benefits of the alternative approaches to delivery (Table 5-7).

We are mindful, that the nub of the Montgomery Case was that [name] had not been adequately appraised of the risks to the fetus, of a vaginal delivery, for a short stature woman, with a large for gestational age fetus. It is important that all women who may be eligible are offered the opportunity to participate in the study, therefore we will ensure the participant information sheet presents the potential risks and benefits clearly accessible format. Our PPI co-applicants are leading on the development of all participant facing materials, together with, a medical ethicist and obstetricians to ensure women are informed. In addition, our participant information sheet, participant information leaflet, consent form and letter to bereaved women have been reviewed and revised by editors from the Plain English Campaign and they have all received a Crystal Mark. Translations will be available for women not fluent in English/Welsh. We will also develop a web based resource for women who would like more detailed information.

**Table 5 Risks of Vaginal Delivery with a Big Baby**

Risks to Baby	Risks to Woman
We do not know for certain how many big babies will experience shoulder dystocia. We estimate that up to one in 25 big babies will experience shoulder dystocia and will need extra help to deliver their shoulders. Most babies who experience shoulder dystocia will have no long-term effects.	Sometimes the labour can be longer for bigger babies. In the UK 15 in 100 women who are planning to have a vaginal birth will need to have an emergency Caesarean section (please see table 7 below). Some women may need to have a forceps or ventouse (suction) delivery.
One in 10 babies who experience shoulder dystocia will have stretching of the nerves in the neck. This is called brachial plexus injury and can cause loss of movement in the baby's arm. The most common type of brachial plexus injury is Erb's palsy. For one in 10 babies with a brachial plexus injury, the loss of movement will be permanent.	Three in 100 women will have a tear to their vagina that extends into the back passage. This could affect their bowel control if the tear is not identified and repaired.
In babies who experience shoulder dystocia, one in 10 may have a fracture to their collarbone. Four in 100 babies who experience shoulder dystocia may have a fracture to their arm. These heal well.	Sometimes women with a big baby may experience heavier bleeding after the baby is born. In rare cases, some women may need a blood transfusion.
Very rarely, a baby may suffer brain damage if they did not get enough oxygen during the birth because of shoulder dystocia.	

**Table 6 Risks of Induction of Labour with a Big Baby**

Risks to Baby	Risks to Woman
Inducing labour at 38 weeks is safe for the baby. There is some evidence that inducing labour earlier can lead to jaundice in the baby. This usually has no long-term effects.	Often women who have labour induced will find their labour is longer and more painful than for women who go into labour naturally.
This trial aims to find out if inducing labour early, at 38 weeks, reduces the chance of shoulder dystocia. If the baby experiences shoulder dystocia, the possible complications are shown in table 1.	If the woman has a vaginal birth the risks are shown in table 1. Having labour induced can increase the risk of a tear to the vagina that extends into the back passage.
Babies who are born one or two weeks early are slightly more likely to need extra help at school, for example help with reading. This would affect less than one baby in every hundred born at 38 weeks compared to 40 weeks.	Sometimes if the woman is induced she may need an emergency Caesarean section, and the risks of this are shown in table 7.

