### 2.2.3 Secondary objective

To evaluate whether: standard care increases the risk of neonatal birth injury, induction increases the risk of infant complications related to prematurity and induction increases the risk of birth injury to the mother.

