**Table 12 - Serious Adverse Event Taxonomy**

Relationship to trial intervention*	Description
Unrelated	There is no evidence of any causal relationship.
Unlikely to be related	There is little evidence to suggest there is a causal relationship (e.g. the event did not occur within a reasonable time after the trial intervention). There is another reasonable explanation for the event (e.g. the patient's clinical condition, other concomitant treatment).
Possible relationship	There is some evidence to suggest a causal relationship (e.g. because the event occurs within a reasonable time after the trial intervention). However, the influence of other factors may have contributed to the event (e.g. the patient's clinical condition, other concomitant treatments).
Probable relationship	There is evidence to suggest a causal relationship and the influence of other factors is unlikely.

Definitely related	There is clear evidence to suggest a causal relationship and other possible contributing factors can be ruled out.
---------------------------	--

\* This will always be **unrelated** if the woman went into spontaneous labour, was in the standard care group or had an elective C-Section prior to onset of labour

**Table 13 - Expected Serious Adverse Events (events that have been previously documented to have occurred in women who have a medical induction of labour)**

Woman
In-patient admission* for postnatal wound infection
In-patient admission for postnatal sepsis/possible sepsis
In-patient admission for postnatal urinary tract infection
In-patient readmission for secondary PPH/retained products of conception
In-patient readmission for vulval haemorrhage
In-patient readmission for genital tract infection
In-patient (re)admission for pre-eclampsia
In-patient readmission for thrombosis
In-patient readmission for epilepsy
In-patient admission for reduced fetal movements
Baby
Cyanosis
Poor SATs
Grunting
Respiratory morbidity
Prolonged hospitalisation/in-patient readmissions for respiratory support

\* A hospital admission is defined here as an overnight stay in the hospital.

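### Table 6 assures women without qualification that induction at 38 weeks is safe for the baby, a question the trial itself sets out to test, and its baby column names no breathing problem

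*Protocol*

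**What the plan says.** Section 1.7 says that women joining must be told about "the possible risks and benefits of the alternative approaches to delivery (Table 5-7"), so Tables 5 to 7 are the protocol's statement of what women should know.

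The baby column of Table 6 has three entries:

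- The first opens with "Inducing labour at 38 weeks is safe for the baby" and continues: "There is some evidence that inducing labour earlier can lead to jaundice in the baby". It adds that this usually has no lasting effect.
- The second states the trial's purpose and refers the reader on: "If the baby experiences shoulder dystocia, the possible complications are shown in table 1". These are complications of shoulder dystocia, not of induction.
- The third says: "Babies who are born one or two weeks early are slightly more likely to need extra help at school, for example help with reading". It puts the effect at under one baby per hundred, comparing birth at 38 weeks with birth at 40.

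The aim in section 2.2.1 covers possible harms as well as benefits of induction at 38+0 to 38+4. Section 2.2.3 asks, among other things, whether "induction increases the risk of infant complications related to prematurity". Section 2.9.2.1 lists respiratory morbidity as a neonatal outcome. The prematurity composite in section 2.9.2.4 has two components, phototherapy and respiratory support.

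Table 13 (section 4.3) lists expected serious adverse events, described as "events that have been previously documented to have occurred in women who have a medical induction of labour". Its last baby entry is "Prolonged hospitalisation/in-patient readmissions for respiratory support".

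**The concern.** A protocol cannot give women a safety statement as settled fact and also make the same matter a secondary objective. Table 6 says nothing about the uncertainty that section 2.2.3 exists to resolve.

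The omission is also uneven. For safety reporting, the protocol treats neonatal breathing events as already known after induction. In the table written to explain the risks of induction, the baby column does not mention them.

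What is at stake is the quality of consent. The protocol sets itself a high standard here: sections 1.6 and 1.7 invoke the Montgomery judgment and the duty to explain risks and benefits. An unqualified assurance in the induction table falls short of that standard, whatever the trial eventually finds.

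**Working it through.** The protocol gives no figure for this point, so the check compares its own statements.

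| Place | Treatment of infant harm from induction at about 38 weeks |
|---|---|
| Table 6, baby column, first entry | Safety stated as fact; jaundice then linked to inducing earlier |
| Table 6, baby column, third entry | Small effect on schooling conceded for birth at 38 versus 40 weeks |
| Section 2.2.1 | Harms at 38+0 to 38+4 are to be investigated |
| Section 2.2.3 | Prematurity-related infant complications are an open question |
| Sections 2.9.2.1 and 2.9.2.4 | Respiratory morbidity and respiratory support are measured |
| Table 13 | Serious breathing events in the baby are expected after induction |
| Table 7 | Breathing difficulty in one baby in 10, given as a risk of caesarean |

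1. **Assurance against objective.** The Table 6 sentence and section 2.2.3 concern the same intervention at the same gestation. One treats the answer as known and the other as unknown. Table 6 also qualifies itself only two entries later.

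2. **Composite against disclosure.** Of the two components of the prematurity composite, phototherapy has a counterpart in Table 6 (jaundice). Respiratory support has none in the baby column. One of two is covered.

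3. **Table 13 against disclosure.** Table 13 has five baby entries: cyanosis, low oxygen saturation, grunting, respiratory morbidity, and prolonged stay or readmission for respiratory support. All five concern breathing or oxygenation. None appears in the baby column of Table 6.

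4. **Consequence of being listed as expected.** Under section 4.3, expectedness is assessed once the site or the sponsor judges an event possibly, probably or definitely related. Only events that are both related and unexpected are expedited. The footnote to Table 12 makes every standard-care event unrelated. Table 13 therefore operates only on events attributed to the intervention, and a listed breathing event would ordinarily not be expedited.

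5. **Indirect route.** The woman's column of Table 6 mentions emergency caesarean and points to Table 7, where breathing difficulty appears. A woman following that route meets it as a consequence of caesarean, not of birth at 38 weeks.

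**The case against.** The strongest reply is that Table 13 does not contradict Table 6. It is a reference list for judging expectedness and records that events have occurred in induced women. Its maternal half includes readmission for epilepsy and admission for pre-eclampsia, so it cannot be read as a list of harms caused by induction. This stands. The documents do not show that induction at 38 weeks raises the rate of breathing problems. They also give no support for removing the respiratory entries from Table 13, although a reader who took it as a causal list might want that.

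Other replies stand in part:

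- Section 1.3 attributes increased prematurity risk to induction before 38+0, and in lay use the word safe may mean only that serious or lasting harm is not expected. This may explain the sentence. It does not justify stating it without qualification while section 2.2.3 tests the matter from 38+0 onward.
- The participant information sheet is not shown. The lay style of Table 6 suggests shared text, as do its references to a table 1 that in the protocol lists the Trial Management Group. That remains an inference. The protocol also provides for discussion with a trained clinician and a web resource.
- Expected status removes only expedited reporting. Under Table 11, neonatal unit admission must still be reported immediately to the trials unit. Section 4.3 considers specificity and severity, so an unusually severe event may still count as unexpected. The DM(E)C reviews accumulating outcomes.

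A reader might also infer that the tables favour induction over standard care and so draw control women towards asking for it, diluting the contrast. The documents do not support this. Table 5 describes vaginal birth in either arm, and Table 6 carries those risks over. Table 6 also adds disadvantages of induction for the woman: longer and more painful labour, more severe tears and emergency caesarean. Nothing in the protocol links the safety sentence to requests for induction.

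**Conclusion.** The point holds as a fault of wording and disclosure. One unqualified sentence in the consent-related risk tables conflicts with the aim, a secondary objective and a composite outcome. The same table's baby column is silent on breathing problems that the protocol treats as expected after induction. It would be wrong to conclude that induction at 38 weeks is unsafe, since the documents contain no evidence of excess risk.

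The information concerns all 4,000 women to be randomised, and also those who read it and enter the cohort instead (an estimated 3,000). The protocol gives no respiratory rate for induction at 38 weeks, so no number of affected babies can be calculated. Design, sample size and analysis are unaffected.

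The finding about the protocol text rests on nothing outside the document. Any statement about what women actually read assumes that the participant information sheet follows Table 6.

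**What to change.** Reconcile Table 6 with sections 2.2.1, 2.2.3 and 2.9.2.4 and with Table 13. Replace the safety sentence with wording such as: whether induction at 38 weeks increases short-term problems for the baby, including jaundice and breathing problems that may need hospital treatment, is one of the questions this trial will answer. Leave Table 13 as it stands.

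Check that the participant information sheet and the web resource say the same, and correct the references to table 1 in the same amendment.

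The cost is a wording amendment with ethics approval and reissue of any affected participant materials. Uptake might fall slightly; the documents give no basis for estimating by how much.
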